**study duration: 01/07/2018 to 31/12/2019**

**EXECUTIVE SUMMARY (Limited to one A4 page and 400 words)**

- Aim and Objectives
- Target Group and Size
- Deliverables
- Key Milestones
- Total Financial Support Requested

- **Aims and Objectives:** This project aims to design and implement a school-based 3-staged physical activity (PA) intervention programme to reduce obesity among adolescents with mild and moderate intellectual disability (ID) in Hong Kong. Specifically, the objectives of the project are:
  1. To reduce body mass index (BMI) among a sample of overweight and obese adolescent children with ID in local special schools;
  2. To reduce % body fat among the sample;
  3. To reduce waist-to-height ratio among the sample;
  4. To reduce overweight and obese status among the sample;
  5. To improve PA levels among the sample.
- **Target Group and Size:** The target population of the project will be adolescents with mild and moderate ID (aged 12- 18 years) who are overweight and obese. Sixty-four overweight and obese students from 4-6 special schools will be recruit (32 in intervention group and 32 in control group).
- **Deliverables:** Expect for the final project report, a manual of the intervention will be generated after completion of the project, with contents covering but not limited to background introduction, how to prepare, implement, and wrap up the intervention. We will also record what components of the intervention worked and what did not. We will present our findings in at least one international conference and publish at least one article in peer-reviewed international journals. If effective, the intervention programme will be run independently by the participating schools after the funding period. It can also be disseminated in other special schools and normal schools to reduce obesity among their students with ID. We will integrate the programme into our courses. Thus, our students can continue delivering the programme in their working schools after graduation. Last but not the least, we will share all deliverables via Facebook and Instagram, which can be used for learning and sharing by schools, parents and other stakeholders in future.
- **Key Milestones:**
  - 01/07/2018 – 31/08/2018 Preparation (literature review, development of intervention plan, and data collection tools)
  - 01/09/2018 – 30/09/2018 Recruitment of participants, pre-intervention measurements
  - 01/10/2018 – 30/06/2019 Intervention, post-intervention measurements
  - 01/07/2019 – 30/09/2019 Data entry, data analysis
  - 01/10/2019 – 31/12/2019 Report and paper writing
- **Total Financial Support Requested:** HK\$ 334,520

### 13. PROPOSED PROJECT

(a) Title: School-based physical activity intervention for obesity among adolescents with intellectual disability in Hong Kong

(b) Justification for conducting the project:

(i) Health needs of the local community (supported by published data or relevant experiences)

Childhood obesity is a major threat to public health internationally, not only because of its well-documented adverse health effects in both childhood and later adulthood, but also its rising trend in prevalence rate over the past decades (Lakshman 2012). The transition from adolescence to young adulthood is recognized as a particularly high-risk period for weight gain, as this critical period is associated with unhealthy lifestyle, including decreased physical activity (PA) levels, increased sedentary time, and decreased diet quality (Nelson, 2008). There is clear evidence that unhealthy lifestyle and obese status established in adolescence continue into adult life and ultimately contribute to early mortality.

Children with intellectual disability (ID) refers to those with significantly reduced ability to understand new or complex information, to learn new skills (impaired intelligence) and to cope independently (impaired social functioning), which starts before the age of 18 years (before adulthood) and has a lasting effect on development. According to the 10th International Classification of Diseases (ICD10), the severity levels of ID are mild (intellectual quotient (ID) of 50-69), moderate (35-49), severe (20-34), and profound (<20). It is estimated that about 1% to 1.25% of the world population are living with ID (Hutzler 2010). In Hong Kong, the latest data indicated that the number of intellectually disable youth aged 15-24 years were 8,141 in 2012, about 0.90% of the whole population in the same age group (Commission on Youth 2014).

It is suggested that children with ID might be more vulnerable to obesity compared to their general counterparts, as they tend to be less active and less empowered to choose and take healthy behaviours (Ptomey 2015; San 2016). We conducted a cross-sectional study among 558 children with mild and moderate ID from 12 special schools in Hong Kong in 2015 (Gao 2016). Results of the study revealed that the prevalence rate of overweight and obesity among the children with ID was 1.5 times that of local general children (31.3% vs. 20.3%, Gao 2016; School Health Service 2012). More adolescents with ID (aged 13 and above) were overweight and obese compared to younger children with ID (aged 6-12 years). Near half of the children (48.3%) spent four and more hours per day in sedentary behaviours, whilst only one tenth of them (10.1%) met the recommended moderate to vigorous PA (MVPA) level of 60 min/day by the WHO. Our results confirmed the higher risk for obesity among adolescents with ID than their general counterparts. There is an urgent call for effective intervention to reduce obesity among this population, in which PA promotion should be involved and regarded as the top priority.

Our previous study covered more than one third of all local schools for children with mild and moderate ID (12 out of 31 schools). By communicating with contact persons of the study schools (including PE teachers, directors of academic affairs, and principals), we obtained the following insights of current situations: (1) most of the contact persons perceived obesity as a health problem for their students; (2), they perceived that, like typically developing children, insufficient PA and unhealthy diet contributed to the epidemic of obesity among children with ID. However, there were additional risk factors among those special children; (3), most of the participating schools encouraged their students to do more exercises. However, the children's PA behaviour and obesity did not change much; (4), they agreed that a solid PA programme might be promising to reduce obesity. Such programme must be designed to address those children's special needs (such as limited intellectual functioning and adaptive behaviour).

(ii) Literature review on others' strategies to address these needs

Numerous studies among general child population have suggested that increasing PA is an effective intervention to reduce obesity (Gao 2008; Waters 2011; Lavelle 2012; Sobol-Goldberg 2013), as it plays an important role in energy balance and regulation of body weight, through increased energy expenditure, improved appetite control, and reduced energy intake (Prado 2015). Schools are considered an ideal environment for delivering such interventions to children, as they spend most of their waking time at school and have access to school facilities for exercise (Waters 2011). Several meta-analyses have demonstrated that school-based interventions (PA only or combined with dietary intervention) are effective to reduce body mass index (BMI) (Waters 2011; Lavelle 2012; Sobol-Goldberg 2013). Interventions used PA in isolation produced a significant BMI reduction of  $-0.17 \text{ kg/m}^2$  in a recent meta-analysis (Lavelle 2012). There is a gradually increasing voice suggesting interventions addressing a single behaviour be more effective to those targeting multiple behaviours simultaneously (Schulz 2015). PA may be more preferred than diet to be the gateway behaviour, given its additional effects on improved appetite control and reduced energy intake (Carraça 2013, Harris 2015, Tucker 2002). In addition, interventions addressing overweight and obese children achieved larger effects than those delivered to all children (reduced BMI:  $-0.35 \text{ kg/m}^2$  vs.  $-0.16 \text{ kg/m}^2$ , Lavelle 2012). Sobol-Goldberg (2013) suggested that long-term school-based interventions were more effective compared to short-term interventions.

(iii) Scientific evidence supporting the strategies to address these needs proposed in this project

Different from those for the typically developing children, PA interventions for children with ID are very scarce, though they are even more vulnerable to obesity. Moreover, previous studies in this population have mainly aimed to test the effectiveness on physical fitness (Shin 2012). A recent meta-analysis on eight PA interventions for individuals with ID at all age groups revealed no significant effects on body weight and body composition, though some studies reviewed in the meta-analysis reported effective (Harris 2015). However, the authors concluded that the results were inconclusive as the published studies and participants involved were inadequate. More intervention studies should be conducted to make up the knowledge gap and PA interventions with a long-time duration might be promising (Harris 2015). There were two interventions for adolescents with ID in that meta-analysis, both of which had a duration less than 10 weeks and reported non-significant results (Elmahgoub 2011; Gonzalez-Aguero 2011). A recent study evaluated effects of a 9-month PA intervention among 23 overweight/obese adolescents with ID, in which intensity was gradually increased to their special needs (Salaun 2014). Results from that study indicated that the programme was effective to reduce waist circumference, waist-to-height ratio, and % body fat. However, its pre-experimental study design (without a control group) makes it difficult or impossible to rule out alternative explanations than the intervention itself.

In summary, (1) children with ID are at high risk for obesity, especially adolescent children; (2) PA interventions with a longer duration are effective to reduce obesity among typically developing child population and might be promising among those with ID; (3) children's special needs should be taken into consideration in the PA interventions; (4) children studying in local special schools have no pressure for academic study, which makes implementation of a long-term school-based PA intervention reasonable and feasible. In addition, some principals of the study schools in our previous study expressed their demand and willingness to reduce obesity among their students.

(c) Aim and Objectives:

This project aims to design and implement a school-based 3-staged PA intervention programme to reduce obesity among adolescents with mild and moderate ID in Hong Kong. Specifically, the objectives of the project are:

1. To reduce BMI among a sample of overweight and obese adolescent children with ID in local special schools;
2. To reduce % body fat among the sample;
3. To reduce waist-to-height ratio among the sample;
4. To reduce overweight and obese status among the sample;
5. To improve PA levels among the sample.

(d) Project Plan:

[figure not shown]
(i) Target group

The target population of the project will be adolescents with mild and moderate ID (aged 12- 18 years) who are overweight and obese. We will adopt a randomised controlled trial (RCT) design and recruit 64 overweight and obese students from 4-6 special schools, and then randomly and equally assign them into the intervention and control groups (32 in each group). This sample size can test an effect size of  $0.722 \text{ kg/m}^2$  (mean difference in change of BMI divided by pooled standard deviation), with an attrition rate of 20%. The selection criteria of participants include: (1) children with mild and moderate ID; (2) aged 13-18 years old; (3) being overweight or obese; (4) without physical disability; (5) without medical predispositions towards obesity (genetic syndrome or drug treatment) that could interfere with the results of the study; and (6) without contraindications for regular physical activity (e.g. asthma, heart disease). A written informed consent will be obtained from their parents/guardians in advance.

(ii) Implementation plan

*1. Description of intervention:*

The PA intervention will be modified from an adapted physical activity (APA) programme for obesity management among adolescents with ID (Salaun 2014). APA programmes aim to promote PA and health for people in special needs, such as people with ID. In this study, the APA programme will be carefully designed based on a comprehensive pre-intervention assessment of each participant, and then to address their individual needs in learning and adaption. It will comprise three stages of PA training at school and each stage will consist of simple and fun endurance and strength-building exercises, gradually increasing in duration and intensity, at a frequency of two sessions per week, and last for about three months (Figure 1). Two exercise sessions per week will give participants enough time to recover. A total time period of nine months was determined due to the following two considerations: (1), children with ID need more time to learn and adapt to a PA programme. Previous studies suggested that a 9-month APA program was suitable and effective to reduce obesity among children with ID (Salaun 2014); (2), local special schools usually plan their activities on a basis of an academic year, which is about 9 months.

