The working load will be individualized and determined based on each participant's PA level measured at the first beginning of each stage. On each stage, each participant will be given about four weeks to adapt the training programme, when the working load and duration will be gradually increased to reach the target intensity and duration (e.g.: 30-40% HRRmax for 30 minutes on Stage 1). The strength-building component in each session, consisting of upper and lower limbs resistance training, will play an important role in improving basal metabolic rate (to speed up fat burning) and preventing physical activity related injury (PARI). The types of exercises in the intervention will be designed by both the research team and PE teachers in the study schools to eliminate the participants' boredom, avoid their attention deficit, and then to enhance their adherence to the intervention. A research assistant (RA) and the PE teachers in the study schools will deliver the intervention to the participants. The participants will also be provided with positive reinforcement and clear feedback to improve comprehension and increase confidence during exercises.

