### (iii) Contingency / alternative plan if any problem encountered during implementation

During the intervention, any participant, no matter in which group (intervention or control), will be asked to suspend or even cease participation if being proved not to be suitable for the study any more due to any reason. For instance, if a participant is caught by a bad cold, his/her situation will be evaluated by both researchers and teachers on spot. Sh/e will be asked to keep the original plan, undertake some low-intensity activities, or skip the planned PA session, according to evaluation results. In addition, the case will be recorded and considered in data analysis and result interpretation later on. For a participant with an attendance rate below than 80%, his/her data will be excluded from data analysis. An attrition rate of 20% was therefore involved in sample size estimation to ensure a sufficient power for data analysis. In addition, intention-to-treat analysis will also be performed to avoid bias from the withdrawals.

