### (vii) Results analysis

IBM SPSS Statistics 23 will be used for data analysis. Continuous variables (e.g., BMI) will be presented with mean (standard deviation, SD) and/or median (interquartile rage, IQR) values. All continuous variables pre-intervention will be tested for between-group differences using independent sample t-test. Normality will be checked by QQ-plots, and tested for equal variance assessed by Levene's test. If skewed, the data will be logarithmically transformed before applying t-test.

A general linear model two-way repeated measure ANCOVA will be used to compare significant differences in the changes in the continuous outcome variables between the two groups, where group and time are the two factors of interest (Elmahgoub, 2011). Variables will be selected in a stepwise manner and only those with  $p < 0.1$  kept in the final models. A significance level of 0.05 will be adopted (two-tailed test). Intention-to-treat analysis will be adopted and performed to avoid bias from withdrawals or protocol deviations.

[Word Count: 2788 ]

(e) Existing Facilities:

We have all facilities needed in this project, including stadiometers, digital balance scales, Body stat 1500 MDD, Polar T31, ActiGraph accelerometers, questionnaires of subjective measurements of PA and eating habits.

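### The plan states no stratification by school and does not pre-specify school in the model, although training and routine PE run school by school; the cost is chance imbalance and some precision, not bias

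*Combined protocol and SAP*

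**What the plan says.** Section 13(d)(i), Target group, sets out to "recruit 64 overweight and obese students from 4-6 special schools". All it says about how these students are allocated is that the team will "randomly and equally assign them into the intervention and control groups (32 in each group"). No stratification, blocking or within-school draw is described there or elsewhere, and no method of generating the sequence is given.

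The school matters to both arms. Under Description of intervention, "A research assistant (RA) and the PE teachers in the study schools will deliver the intervention to the participants", and those teachers also help to design the exercises. Under Description of control, the other arm has its usual PE classes.

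Section 13(d)(vii), Results analysis, plans a repeated-measures ANCOVA "where group and time are the two factors of interest". Further variables are chosen stepwise and kept at p < 0.1, but the candidates are not listed. School is not named there, nor among the control variables listed in section 13(d)(vi), Evaluation plan, although that list is open-ended.

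**The concern.** School is an obvious potential source of variation in BMI change and physical activity, because teachers, exercise content and routine PE can all differ from school to school. With 4-6 schools there are only about 11-16 participants in each. A draw that ignores school can leave one school mostly in the intervention arm and another mostly in the control arm. In the allocation actually obtained, differences between schools would then be partly confounded, by chance, with the difference between arms. A school could also be left with very few children to form a session group, or very few concurrent controls.

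If school does explain part of the outcome and is not in the model, that variation stays in the error term. A stepwise rule at p < 0.1 does not secure its place, because a moderate school effect can easily miss that threshold in a sample this small.

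**Working it through.** **Inputs from the documents.** 64 students, 32 per arm, 4-6 schools, standardised effect 0.722 and 20% attrition (section 13(d)(i); the effect is labelled kg/m² but defined as a ratio to the SD); "A significance level of 0.05 will be adopted (two-tailed test") (section 13(d)(vii)). No power figure is stated, only that "An attrition rate of 20% was therefore involved in sample size estimation to ensure a sufficient power for data analysis" (section 13(d)(iii)).

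**Assumptions.** Near-equal school sizes, and a school share of variance (ICC) of 0-20%. The documents give neither.

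**1. The plan's own figure.** At two-sided 0.05, 80% power and d = 0.722, a two-sample t-test needs 32 per arm before attrition, and 32/0.8 = 40 per arm after it. So 32 per arm gives about 80% power only if nobody is lost. That is a separate issue, but it means power should be shown both at 32 and at 32 × 0.8 = 25.6 per arm.

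**2. Balance under a pooled draw.** If 32 of 64 students are drawn regardless of school, the numbers k_j assigned to intervention in schools of size m_j have probability ∏C(m_j, k_j)/C(64, 32). Adding this up over all allocations in which at least one school splits 2:1 or worse gives:

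| Schools | Sizes | 2:1 or worse | 3:1 or worse |
|---|---|---|---|
| 4 | 16 each | 41.7% | 14% |
| 5 | 13, 13, 13, 13, 12 | 69.4% | 28% |
| 6 | 11, 11, 11, 11, 10, 10 | 74.5% | 28% |

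Simulated draws agree to within about a point (42%, 69-70%, 74-75%). With assumed unequal sizes (24/20/12/8 or 20/14/10/8/7/5), 2:1 or worse has probability about 54% or 82%.

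**3. How far imbalance moves the estimate.** With school effects u_j, the shift is Σu_j(2k_j − m_j)/32. Its mean is zero. For four schools of 16, Var(2k_j − m_j) = m(64 − m)/63 = 16 × 48/63 = 12.19, so the SD of the shift is √(ICC × 4 × 12.19/1024) = √(0.0476 × ICC). In units of the outcome SD this is 0.05, 0.07 and 0.10 at ICC 0.05, 0.10 and 0.20. The ordinary standard error is √(2/32) = 0.25.

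**4. Power.** Without school, the noncentrality is d√(n/2): 0.722 × √16 = 2.888 on 62 df gives 81.1%, and 0.722 × √12.8 = 2.583 on 49.2 df gives 71.6%. With balanced schools and adjustment, d becomes 0.722/√(1 − ICC) and 3-5 df are deducted:

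| School share of variance | Adjusted d | 32 per arm | 25.6 per arm |
|---|---|---|---|
| no school term | 0.722 | 81.1% | 71.6% |
| 0% | 0.722 | 81.0% | 71.5% |
| 5% | 0.741 | 83.0% | 73.7% |
| 10% | 0.761 | 84.9% | 76.0% |
| 20% | 0.807 | 88.8% | 80.7% |

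A simulation with 4 schools and 52 completers (3,000 runs, Monte Carlo error about 0.8 points) compared a pooled draw without school against a stratified draw with school. Power was 72.4% vs 72.9% (ICC 0.02), 72.6% vs 73.8% (0.05), 73.9% vs 77.3% (0.10) and 73.6% vs 80.5% (0.20).

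**5. Why the two parts belong together.** Adjusting for school after a pooled draw inflates the variance of the estimate by a factor averaging 1.05 (4 schools), 1.07 (5) or 1.09 (6), because unbalanced schools carry less information. At ICC 0.05 with 4 schools, 0.95 × 1.052 = 1.00: adjustment alone gains nothing. Stratifying as well removes the inflation.

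**The case against.** Three stronger readings are tempting, and the documents support none of them.

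- *The plan randomises all students as one pool.* It does not say so. It is silent on how the draw is made. A pooled draw is the natural reading, but within-school allocation is not excluded.
- *School is excluded from the analysis.* Group and time are named as the factors of interest, and the stepwise step allows others. School could enter; its place is simply not secured.
- *Lopsided schools bias the result.* Students are randomised individually, so the estimate is unbiased. With no school-by-treatment variation, simulated type I error without a school term is 4.8-5.3%. The imbalance percentages count lopsidedness, not harm: a 5:11 split in one school of 16 counts. Step 3 shows that the resulting shift is small beside the standard error, which already carries it.

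It can also be said that the precision gain rests wholly on an undocumented ICC and is only about 0-2 power points at 0.05 or below; that the power figures come from a two-sample comparison, not the planned repeated-measures model; and that a school main effect alone does not remove between-school variation in change over time. All of this stands. It limits the size of the point and shapes the fix. It does not remove the case for a step that costs next to nothing.

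**Conclusion.** The point holds as an inexpensive improvement, not as a flaw that invalidates the trial. Stratification by school is not stated and school is not pre-specified, in a design where both conditions depend on the school.

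The chance of at least one school splitting 2:1 or worse (about 42%, 70% or 75%) assumes a pooled draw and near-equal schools, but needs no ICC. The change in power does depend on the ICC: at 32 per arm it runs from a loss of about 0.1 point if school explains nothing to a gain of about 8 points (88.8 − 81.1 = 7.7) at a 20% share, and after attrition to about 9 points (80.7 − 71.6 = 9.1). The documents do not show where in that range the trial lies. The trade is uneven in favour of the change, more so because power is only about 72% once the plan's own attrition is applied.

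**What to change.** - **Allocation (section 13(d)(i)).** State that students are randomised 1:1 within each school, for example by permuted blocks, or by one draw per school once its participants are enrolled and measured at baseline. This must be settled before allocation, since imbalance cannot be undone later. If stratification was always intended, say so.
- **Model (section 13(d)(vii)).** Include school and school-by-time as forced terms outside the stepwise selection, for BMI and the other continuous outcomes. Alternatively, use school as a fixed factor in a model of BMI change. In the repeated-measures form a school main effect alone is not enough, because the comparison is of change over time.
- **Reporting.** Show results by school descriptively.

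The cost is a sentence on allocation and the model terms: 3-5 degrees of freedom in a model of change, about 0.1 power point if school explains nothing, and no added participants or staff.

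Two limits remain. Very small schools will still have small arms: a school contributing 5 students would have 2 or 3 in each. A school term also does not address treatment effects that differ between schools. With an assumed school-by-group variance of 0.05 SD² and 4 schools, simulated type I error was about 6-8% with or without it.

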## 2. Description of control:

The participants in the control group will receive routine PE classes as usual during the intervention period (in the academic year of 2018/19).

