### (v) Indicators and targets

Outcome indicators will consist of BMI, % body fat, waist-to-height ratio, body weight status, and PA levels. Taking BMI as an example, we expected to achieve an effect size of  $0.722 \text{ kg/m}^2$  (mean difference in change of BMI divided by pooled standard deviation) via the intervention.

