3. Incentives for participants: in order to increase the participation rate and decrease the attrition rate, a token incentive of a HK\$100 coupon (e.g. supermarket coupon) will be given to the participants competing the whole study. Thus, a total cost of HK\$6400 was estimated. In addition, rewards (e.g. stickers) will be given to the participants who complete each intervention session (a total of 72 sessions). A total of HK\$2000 was then estimated. Governance system: We will purchase coupons and stickers via the Finance Office (FO) of our university. We will ask a parent/guardian of each participant sign on the record sheet for receiving a coupon of HK\$100. The FO will monitor the disbursement of incentives to ensure accountability and traceability.
4. Conference: we will present our findings on at least an international conference. A total cost of HK\$10000 was then estimated.
5. Publication costs: We will publish at least one article in an international

peer-reviewed journal. We want it to be open access and freely available online. Open access publishing is a charged service. For example, a quality journal levies an article-processing charge of USD2785 (around HKD 21723) for each article accepted for publication. A total cost of HK\$20000 was then estimated.

6. Transportation cost: the research staff will travel between schools and office to implement the intervention. A total cost of HKD 8640 was estimated, at a rate of HKD30/travel, 72 travels/person, and 4 persons).

(ii) Estimated revenue or recurrent income (if any) to offset the expenditure of the project  
Nil

(iii) Supplementary sponsorship (monetary or non-monetary) (if any) to cover any expenditure or resource requirement of the project  
Nil

(g) Purpose and Potential:

(i) How will this project enhance your community's capacity to promote health in the long run  

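### The BMI target of 0.722 carries a unit that its own definition rules out, and the power said to survive 20% attrition is never stated (about 71–72% by a simple t-test if 0.722 is standardised)

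*Combined protocol and SAP*

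**What the plan says.** Section 13(d)(i), Target group, sets 64 children, 32 per arm, and says this number can test an effect printed as 0.722 kg/m². The same sentence defines the effect as "mean difference in change of BMI divided by pooled standard deviation), with an attrition rate of 20" per cent. Section 13(d)(v), Indicators and targets, gives the same figure and unit as the expected result, again as a "mean difference in change of BMI divided by pooled standard deviation) via the intervention".

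Section 13(d)(iii), Contingency, excludes children who attend less than 80% of the time and continues: "An attrition rate of 20% was therefore involved in sample size estimation to ensure a sufficient power for data analysis". It gives no power figure, and neither does any other section. The only significance level is in section 13(d)(vii), Results analysis: "A significance level of 0.05 will be adopted (two-tailed test"). The SD of BMI change is named as a divisor but never given a value.

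**The concern.** There are two linked problems.

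**The unit.** A ratio of a mean difference to an SD cannot be in kg/m². The two readings agree only if the SD of BMI change is exactly 1 kg/m², which the plan does not say. Read as standardised, 0.722 means 0.36 to 1.08 kg/m² for an SD of change between 0.5 and 1.5 kg/m² (assumed range). The same figure serves both to size the trial and to state the expected result, so the ambiguity affects design and interpretation.

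**The power.** A reader of sections 13(d)(i) and 13(d)(iii) will conclude that adequate power remains after 20% loss. Without a stated power this cannot be checked. The most direct calculation puts the post-loss figure well below the 80% usually expected. That 80% is a convention assumed here, since the plan names no target.

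**Working it through.** **Inputs.** From the plan: effect 0.722, 32 per arm, 20% attrition (13(d)(i)); two-sided α = 0.05 (13(d)(vii)). Not in the plan: power, SD of change, any correlation.

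**Formula.** Two-sample t-test, noncentral t: λ = d × √[n₁n₂/(n₁+n₂)], df = n₁+n₂−2, power = P(|T| > t₀.₉₇₅,df).

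**1. Can 64 be reproduced?** Not strictly, because no power is given. Taking d = 0.722 as standardised, these are the routes tried:

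| Assumed target | Evaluable n per arm | Recruited per arm at n/0.8 |
|---|---|---|
| 80%, two-sided | 31.10 → 32 | 32/0.8 = 40 |
| 70%, two-sided | 24.68 → 25 | 25/0.8 = 31.25 → 32 |
| 80%, one-sided | 24.43 → 25 | 31.25 → 32 |

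So 32 per arm is the two-sided 80% answer before any loss. With a 20% allowance it is reached only at about 70% two-sided power, or at 80% one-sided, which would not match section 13(d)(vii).

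**2. Power for d = 0.722, two-sided 5%.**

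| Situation | n per arm | λ | Power |
|---|---|---|---|
| No loss | 32 v 32 | 0.722 × √16 = 2.888 | 81.1% |
| 20% lost from each arm, rounded up | 26 v 26 | 0.722 × √13 = 2.603 | 72.3% |
| Same, unrounded (32 × 0.8) | 25.6 v 25.6 | 0.722 × √12.8 = 2.583 | 71.6% |
| Same, rounded down | 25 v 25 | 0.722 × √12.5 = 2.553 | 70.6% |
| 20% lost from the intervention arm only | 26 v 32 | 2.735 | 76.7% |
| Same, rounded down | 25 v 32 | 2.705 | 75.7% |
| 20% of all 64 (12.8 → 13), all from the intervention arm | 19 v 32 | 2.493 | 68.6% |

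The effect detectable at 80% power is 0.711 SD with no loss and 0.79–0.81 SD at 26 to 25 per arm.

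**3. What could restore power** (all inputs assumed; 25.6 per arm unless stated).
- Covariate correlated r with the outcome, effect d/√(1−r²), one df fewer: r = 0.3, 0.4, 0.5 gives 76%, 79%, 83%.
- Averaging the changes at T2, T3 and T4 with equal effects, variance factor (1+2ρ)/3: ρ = 0.7, 0.8, 0.9 gives 81%, 78%, 75%. The gain is smaller if the effect builds over the stages.
- Intention-to-treat with all 32 per arm measured: 81% at an undiluted effect. If 20% of the intervention arm gets half the effect (0.8 + 0.2 × 0.5 = 0.9 of d), power is 73%. If that 20% gets none (0.8 of d), it is 62%.

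**4. The raw reading.** If 0.722 is in kg/m², 80% power needs an SD of change of at most 0.722/0.711 = 1.01 kg/m² with no loss, or 0.89–0.91 after 20% loss. At assumed SDs of 0.75, 1.0, 1.25 and 1.5 kg/m², power after loss is 92%, 72%, 53% and 39%.

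**5. Against the plan's own evidence.** Section 13(b)(ii) reports that "interventions addressing overweight and obese children achieved larger effects than those delivered to all children", with a BMI reduction of 0.35 kg/m². A raw 0.722 is 0.722/0.35 = 2.1 times that. A standardised 0.722 equals it only if the SD of change is 0.35/0.722 = 0.48 kg/m². This does not settle which reading was meant.

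**The case against.** **The unit is probably a slip.** Both sections call 0.722 an effect size and both define it as a ratio, so the standardised reading is the natural one. That is fair, and it makes the repair easy. The unit is nevertheless printed in both places, and without an SD the reader cannot rule out the raw reading. The 0.35 kg/m² comparison is context only: the plan does not derive 0.722 from it, and it comes from studies of children in general.

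**Loss may not fall on both arms.** The 20% follows from the attendance rule. The sessions belong to the intervention arm: "rewards (e.g. stickers) will be given to the participants who complete each intervention session (a total of 72 sessions"). For controls, "The participants in the control group will receive routine PE classes as usual during the intervention period". Loss concentrated there is plausible and gives 76–77% if it is 20% of that arm, but 69% if it is 20% of the whole sample. Section 13(d)(i) attaches the 20% to the whole sample and 13(d)(iii) allows withdrawal in either group, so equal loss is also a fair reading.

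**The t-test is not the planned analysis.** The plan specifies a repeated-measures ANCOVA with four measurement times, and "Intention-to-treat analysis will be adopted and performed to avoid bias from withdrawals or protocol deviations". An attendance exclusion does not by itself shrink the intention-to-treat set. This stands: the scenarios above run from 62% to 83%. But the sizing text invokes none of these gains and supplies no correlation, and 13(d)(iii) ties the allowance to the analysis with exclusions.

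**Nothing fails to reproduce.** Correct. With no stated power, 64 is compatible with more than one calculation, and the word sufficient is not contradicted by any figure in the plan.

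**Conclusion.** The concern holds. Two parts are certain from the text: the unit contradicts the definition in sections 13(d)(i) and 13(d)(v), and the claim of sufficient power has no figure behind it. The third part is conditional. For a standardised 0.722, two-sided 5%, an unadjusted t-test and 20% loss in both arms, power is about 71–72% (70.6–72.3% depending on rounding), against 81% with no loss. On that basis the 20% allowance is not delivered at 80% two-sided power. Undocumented gains from covariates, repeated measures or complete follow-up could change this. An error in the sponsor's calculation is not shown. This should be fixed before the sizing statement is relied on.

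**What to change.** Keep 64 children and correct the text.

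- **Sections 13(d)(i) and 13(d)(v):** delete the unit after 0.722. If 0.722 is in fact a raw difference, delete the division by the pooled SD instead and give the SD of BMI change.
- **Sections 13(d)(i) and 13(d)(iii):** replace the bare attrition statement and the claim of sufficient power with the two-sided power before and after 20% loss. For a standardised 0.722 by unadjusted t-test, suitable wording is: *32 per group gives 81% power with no loss and about 71–72% if 20% are lost from each group.*
- **Alternatively,** give the sponsor's own figure, provided it states and justifies the covariate correlation, repeated-measures gain or complete intention-to-treat follow-up it relies on. If 0.722 is raw, compute both figures from the stated SD.

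The cost is wording only. The stated power after loss will look less favourable unless a gain is justified.
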